3. STUDY DESIGN

3.1 GENERAL DESCRIPTION

This is a multicenter, randomized, double-blind, placebo-controlled Phase 3 study in the US

Noven Pharmaceuticals, Inc.

Protocol HP-5000-US-07

Statistical Analysis Plan

Page 14 of 58

evaluating the efficacy and safety of HP-5000 in subjects with OA pain of the knee.

The study will consist of up to a 28-day Screening Phase that will include a Washout Period of current prescription and over the counter (OTC) analgesics; a 12-week Double-blind Treatment Phase, and a 1-week safety Follow-up Phase.

Screening Phase: Subjects will be seen in the clinic where the study will be described to them and will be asked to sign the informed consent form (ICF). No screening procedures may begin prior to obtaining informed consent. After obtaining a written informed consent, subjects will be screened for participation in the study. The target knee for the purpose of the study will be defined as the one which causes the subject more pain than the other knee and will be identified at the Screening visit using the NRS score. During the Screening Phase, subjects will complete a daily electronic diary (eDiary) to record pain severity of their target knee. Subjects who satisfy the entry criteria will be instructed to begin the Washout Period for 7 to 14 days, or at least 5 half-lives, whichever is longer, prior to the Baseline Visit (Day 0).

During the Washout Period, current prescription and OTC analgesics will be discontinued. However, rescue medication (acetaminophen [APAP]) for the treatment of any other aches the subject might experience during the trial, such as headache, reduction of fever, and the target knee pain of OA (not for the non-target knee) will be permitted (a maximum of 2 g/day) except within 3 calendar days prior to the Baseline Visit (i.e., rescue medication is prohibited for 2 days until clinic visit on Day 0 and on the day of Baseline Visit [V3]). During the Washout Period, subjects will complete a daily eDiary to record rescue medication usage in addition to pain severity of their target knee. Following completion of the Washout Period, subjects will return to the clinic for their Baseline Visit (Day 0). Eligible subjects will be randomized to either HP-5000 or placebo in a 1:1 ratio.

Treatment Arm	Treatment
HP-5000	HP-5000 [REDACTED] patch Each patch contains [REDACTED] diclofenac sodium.
Placebo	HP-5000 [REDACTED] Placebo patch Each patch contains 0% [REDACTED] diclofenac sodium.

Double-blind Treatment Phase: Subjects will apply a single patch to the target knee [REDACTED]

[REDACTED] After the removal of the patch [REDACTED], a new patch will be applied to a different site on the target knee. Subjects will be instructed to rotate the patch application site [REDACTED] to alternate sides (inner and outer) of the target knee. During the Double-blind Treatment Phase, subjects will also complete a daily eDiary to record patch application and removal time, adhesion, irritation, discomfort, and pain assessments; and

Noven Pharmaceuticals, Inc.

Protocol HP-5000-US-07

Statistical Analysis Plan

[figure not shown]
Page 15 of 58

amount of rescue medication (APAP) taken daily, if applicable. A maximum of 2 g/day of APAP will be allowed as rescue medication except from Baseline Visit until Visit 4, within 2 calendar days prior to all subsequent visits (V5, V6, V7, and V8), and on the day of the clinic visits (V4, V5, V6, V7, and V8).

NOTE: Subjects are NOT allowed to apply HP-5000 on the non-target knee at any time during the study.

Follow-up Phase: Subjects will have a safety visit approximately 7 days after the Week 12 End-of-Treatment Visit. The investigator or qualified study staff will contact all subjects by phone for continued safety monitoring of AEs. At the discretion of the investigator, subjects may have to return to the clinic for their Follow-up Visit.

Figure 1: A Schematic of the Study Design

Sample Size: Based on the HP-5000 Phase 2 study results, the assumed effect size of the test product in the pivotal study will be about [REDACTED]. The sample size of [REDACTED] subjects per treatment arm (or total of about [REDACTED] subjects) will be included in order to have 80% power to demonstrate statistically significant difference versus placebo using a 2-sided overall Type I Error rate of 0.05.

3.2 SCHEDULE OF EVENTS

The schedule of events can be found in [Section 10.2](#) of the protocol.

Noven Pharmaceuticals, Inc.

Protocol HP-5000-US-07

Statistical Analysis Plan

Page 16 of 58

3.3 CHANGES TO ANALYSIS FROM PROTOCOL

Not Applicable

4. PLANNED ANALYSES

4.1 DATA SAFETY MONITORING BOARD

There will be no Data Safety Monitoring Board for this study.

4.2 INTERIM ANALYSIS

No interim analyses are planned.

4.3 FINAL ANALYSIS

The analyses detailed in this SAP will be performed by [REDACTED] Biostatistics following sponsor authorization of this SAP, Database Lock, Sponsor authorization of Analysis Sets and Unblinding of Treatment.

5. ANALYSIS SETS

Analysis of efficacy and safety endpoints will be performed based on the analysis sets defined in this section. The inclusion/exclusion of subjects from each analysis set will be determined prior to the final analyses (and approved by Noven) based on blinded data review.

5.1 INTENT-TO-TREAT SET[ITT]

Intent-to-treat (ITT) analysis set includes all consented and randomized subjects. Regardless of any protocol deviations and/or treatment compliance, analyses performed on the ITT set will be based on the randomized treatment assignment and all available data. The ITT set will be used as the primary set for analysis of primary and secondary efficacy endpoints. If a subject is randomized incorrectly or is administered the incorrect study drug, analyses of the ITT set will be based on the assigned treatment whereas all analyses of the safety analysis set will be based on the actual treatment.

Noven Pharmaceuticals, Inc.

Protocol HP-5000-US-07

Statistical Analysis Plan

Page 17 of 58

5.2 SAFETY ANALYSIS SET [SAF]

Safety analysis set (SAF) includes all subjects who have had at least 1 patch of double-blind study drug applied and who have at least 1 post-dose safety measurement during the Double-blind Treatment Phase. In the unlikely event that errors may have occurred in treatment arm assignments, then analyses using the SAF set will be based on treatment actually received. The SAF set will be used for the analysis of dermal evaluations and safety endpoints.

6. GENERAL CONSIDERATIONS

6.1 REFERENCE START DATE AND STUDY DAY

Relative study day will be calculated from the date of Day 0, which is the day of Baseline Visit (V3) and will be used to show the start and/or stop days of treatment, study procedures, and assessments.

If the date of the treatment, procedure, or event is on or after the Day 0 date then:

Relative Study Day = (date of variable of interest – Day 0 date) + 1.

If the date of the treatment, procedure, or event is prior to the Day 0 date then:

Relative Study Day = (date of variable of interest – Day 0 date).

If the date of the treatment, assessment, or event is partial or missing, relative study day, and any corresponding event durations will appear missing in the listings.

6.2 BASELINE AND POST STUDY ASSESSMENT

Baseline is defined as the last non-missing measurement taken on or prior to the first patch application date. In the case where the last non-missing measurement and the reference start date coincide, that measurement will be considered pre-baseline if the assessment is planned per protocol to take place prior to first study medication administration.

Post-study assessment is defined as a non-missing measurement taken on or after the date of the last patch removal. In the case where the dates coincide, time of the measurement should be after the last patch removal time to be considered post study assessment. This will be applied to identify post study medications and adverse events.

Noven Pharmaceuticals, Inc.

Protocol HP-5000-US-07

6.3 VISIT WINDOWING CONVENTIONS

Analyses presented by visit or study day will be based on the protocol defined scheduled visits including scheduled, unscheduled, and early discontinuation visits. Visit windows for unscheduled visits and early discontinuation visits are defined in Table A, which provides the mapping of relative day ranges to the scheduled target days and the study periods. If more than one assessment is available in the same 'Range of Relative Study Days' (window), the assessment closest to the Scheduled Target Day will be selected and assigned to that Scheduled Target Day. If two or more assessments are available in the same window and are equidistant from the Scheduled Target Day, the latest assessment will be selected.

All study listings will include scheduled, unscheduled, re-test, and early discontinuation data.

Table A: Mapping of Relative Day Ranges to Schedule Target Day

Study Phase	Study Period	Range of Relative Study Days	Scheduled Target Day
Screening	Screening (Visit 1) Washout (Visit 2)	28-14 days before Day 0 datetime 14-7 days before Day 0 datetime	Day -28 to -14 Day -14 to -7
Double Blind Treatment	Baseline (Visit 3)	After first patch application Day 0 datetime	Day 0
	Week 1 (Visit 4)	1 to 10 days relative to Day 0 datetime	Day 7
	Week 2 (Visit 5)	11 to 17 days relative to Day 0 datetime	Day 14
	Week 4 (Visit 6)	18 to 38 days relative to Day 0 datetime	Day 28
	Week 8 (Visit 7)	39 to 73 days relative to Day 0 datetime	Day 56
	Week 12 (Visit 8)	After the last dose of treatment (patch removal) and before the start of the Safety Follow-up Period (one day after actual Day 84 visit) which will be \geq 74 days after Day 0 datetime.	Day 84

Noven Pharmaceuticals, Inc.

Protocol HP-5000-US-07

Follow-up	Safety Follow-up	>84 days after Day 0 datetime for treatment completers (83 days on-treatment and after last patch removal) and after Day 84 post-treatment assessments or after early discontinuation visit (for subjects who terminated early).	Day 91
-----------	------------------	--	--------

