#### **10.1.5 Early Termination Visit (if applicable)**

Subjects who are discontinued prematurely from study for any reason after Baseline (Visit 3) must complete the Early Termination Visit. If the subject comes for an Unscheduled Visit and a decision to withdraw the subject is made, then the Early Termination Visit procedures will be performed and the Early Termination Visit eCRF will be completed (and not the Unscheduled Visit eCRF).

During this visit the following assessments and procedures will be performed:

1. Perform physical examination.
2. Obtain vital signs measurements.

3. Obtain subject's weight.
4. Obtain blood and urine samples for laboratory testing.
5. Perform a urine pregnancy test.
6. Perform a 12-lead ECG.
7. Administer the WOMAC questionnaire for the target knee.
8. Perform PGA.
9. Perform PGIC.
10. Perform a QOL Questionnaire.
11. Remove the patch on a skin.
12. Instruct a subject to perform the following assessments in the eDiary when they remove the patch at the site:
  - a. Perform and record scoring of the pain of the target knee using the NRS 11-point pain scale
  - b. Record the time of patch removal.
  - c. Record the time of not scheduled complete patch detachment and the reason (if applicable).
  - d. Record the number of tablets of rescue medication used, the time and the reason.
13. Review the subjects' eDiary entries.
14. Collection of unused study drug and rescue medication.
15. Review subject's use of rescue and concomitant medications.
16. Perform drug accountability/reconciliation of study drug and rescue medication. The reconciliation (missing patch, failure of application, unscheduled detachment and application, etc.) will be recorded in the eCRF.
17. Perform dermal safety assessment (irritation, discomfort, and adhesion).
18. Review AEs. The irritation and discomfort reported in the eDiary will be treated as AEs.
19. Record the date and the reason of early termination in the eCRF.

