16.1.4 COMPOSITE STRATEGY ANALYSIS FOR PRIMARY EFFICACY

Composite strategy will be applied to the stratum of subjects experiencing intercurrent events.

For the intercurrent events of study treatment discontinuation due to reasons related to study treatment (AE, LOE, etc.), the obtained WOMAC pain score will be addressed in the analysis by expecting the long-term benefit from the treatment for that subject to be zero from the time of intercurrent event. For the other intercurrent events, rescue medication use within 24 hours of WOMAC assessment, removal/detachment of study patch for more than 24 hours before WOMAC assessment, the obtained WOMAC pain score will not be included in the analysis.

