18.4 ECG EVALUATIONS

The following ECG parameters will be reported for this study:

PR Interval (msec);

QRS Interval (msec);

QT Interval (msec);

RR Interval (msec);

QTcF Interval (msec) [derived by central ECG];

HR (bpm);

Overall assessment of ECG.

Should ECGs be collected in triplicate or multiple assessments on the same day, they will be analyzed as an average of the non-missing measurements on the same day. For the overall assessment, there are three possible results from the central cardiologist: 'Abnormal, Not Clinically Significant', 'Normal', and 'Abnormal, Clinically Significant'. All assessments will be summarized according to the worst non-missing assessment and categorized in the following order, "Normal", "Abnormal, Not Clinically Significant", "Abnormal, Clinically Significant".

The following summaries will be provided for ECG data for each parameter by treatment group and study visit:

Actual and change from baseline at Visit 8 (for quantitative measurements);

Shifts from baseline to worst overall ECG result.

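### SAP 6.3 puts all early-termination assessments through one set of day windows, so ET ECG, weight, laboratory and QOL records land on visits that do not schedule them, and some ET WOMACs are dropped or displace a completed visit

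*SAP*

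**What the plan says.** - **Windowing (SAP 6.3).** "Visit windows for unscheduled visits and early discontinuation visits are defined in Table A". Where several records share a window, "the assessment closest to the Scheduled Target Day will be selected and assigned to that Scheduled Target Day". When records "are equidistant from the Scheduled Target Day, the latest assessment will be selected". The windows are: Week 1 (target Day 7), "1 to 10 days relative to Day 0 datetime"; Week 2 (target Day 14), "11 to 17 days relative to Day 0 datetime"; Week 4 (target Day 28), Days 18–38; Week 8 (target Day 56), Days 39–73; Week 12 (target Day 84), from Day 74. There is no ET or end-of-treatment category and no window specific to an assessment. Listings keep every record.
- **ET visit (Protocol 10.1.5).** It applies to subjects discontinued from the study. It includes "7. Administer the WOMAC questionnaire for the target knee", and also weight, laboratory samples, a 12-lead ECG and the QOL questionnaires.
- **Schedule (Protocol 10.1.3 and 10.2).** Apart from ET, ECG and weight are collected after baseline only at Visit 8 (Week 12). Laboratory tests and QOL are collected only at Visit 6 (Week 4) and Visit 8.
- **Outputs.** SAP 18.4 plans, for quantitative ECG, "Actual and change from baseline at Visit 8 (for quantitative measurements". SAP 18.3 and 18.5 summarise laboratory values and weight by study visit. SAP 16.3.14 and 16.3.15 analyse the QOL scores at Weeks 4 and 12 in an MMRM with visit as an effect.
- **Intercurrent events (SAP 16.1.4).** Treatment-related discontinuation of study treatment is handled by "expecting the long-term benefit from the treatment for that subject to be zero from the time of intercurrent event".

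**The concern.** Table A suits assessments made at every clinic visit. ECG, weight, laboratory tests and QOL are not. A subject who leaves on Day 50 gives an ECG, a weight, laboratory samples and QOL answers, and Table A labels all of them Week 8, where none is scheduled. The ECG then has no place in the Visit 8 table. The weight and laboratory values form a Week 8 row made up of leavers only. The QOL scores either add a Week 8 level to the MMRM that holds only dropouts, or are left out by the programmer; the SAP does not say which.

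WOMAC is collected at every post-baseline clinic visit, so the difficulty there is competition. A subject seen on Day 28 who leaves on Day 36 has two WOMACs in the Week 4 window, and the later one is dropped. Which record survives depends on the day the scheduled visit was attended, not on a stated rule about leavers.

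At stake are the end-of-treatment safety and QOL data of subjects who leave, and whether the last WOMAC of a leaver enters the by-visit analysis.

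**Working it through.** The plan gives no figure to reproduce, so the Table A rule is applied by counting days. Day d means d days after Day 0.

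**Step 1: ECG and weight.** Only the Week 12 window (Day 74 onward) schedules them. ET days that map elsewhere are Days 1–73, so 73 of 83 = 88% of Days 1–83.

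**Step 2: laboratory tests and QOL.** The Week 4 (Days 18–38) and Week 12 windows schedule them. ET days that map to Weeks 1, 2 or 8 are Days 1–17 (17 days) and Days 39–73 (35 days). 17 + 35 = 52; 52 of 83 = 63%.

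**Step 3: WOMAC, scheduled visits on target.** Between-visit days run 8–13, 15–27, 29–55 and 57–83, which is 6 + 13 + 27 + 27 = 73. An ET record is dropped when it shares a window with a completed visit and lies further from target.

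| Last completed visit | ET days dropped | Count |
|---|---|---|
| Week 1, Day 7 | 8–10 | 3 of 6 |
| Week 2, Day 14 | 15–17 | 3 of 13 |
| Week 4, Day 28 | 29–38 | 10 of 27 |
| Week 8, Day 56 | 57–73 | 17 of 27 |
| Total | | 33 of 73 (45%) |

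**Step 4: plus-one day count.** SAP 6.1 adds 1 to the day on or after Day 0. If Table A is read on that scale, each window closes one calendar day sooner, and the counts are 2 + 2 + 9 + 16 = 29 of 73 (40%). In Steps 1 and 2 the totals fall by one day each: 72 of 83 (Days 1–72) and 51 of 83 (Days 1–16 and 38–72, 16 + 35).

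**Step 5: scheduled visit off target.** Protocol 10.2 allows ±7 days at Visit 7. If Visit 7 falls on Day 49, it is 7 days from target. An ET on Days 50–63 is no further away than that (Day 63 ties, and the later record wins), so the ET record replaces the completed Week 8 visit. An ET on Days 64–73 is dropped. If Visit 7 falls on or after Day 56, every later ET up to Day 73 is dropped.

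**Step 6: QOL model.** A subject with an ET record has left the study, so nobody would have both an ET-derived Week 8 QOL score and a Week 12 score. Under the unstructured matrix that SAP 16.1.3 and Appendix 2 use by default, that covariance could not be estimated.

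**The case against.** A reader might infer more: that windowing removes the scores the composite rule needs, leaves Weeks 8 and 12 missing at random from a pre-failure value, and so biases the primary comparison. The documents do not support that.

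- SAP 16.1.4 concerns stopping study treatment, whereas ET visits are for leaving the study. Protocol 8.2.3 (the later of the two versions in the file, whose reason categories SAP section 9 follows) separates the two and strongly encourages subjects who stop treatment to attend the remaining visits. Their Week 8 and Week 12 WOMACs are not affected by this point.
- The SAP does not say that later visits of a leaver are treated as missing at random despite the event. Section 16.1.4 can be read as setting benefit to zero at all visits after it, in which case the ET value matters little. How zero benefit is computed is left open, but that is a separate gap.
- Section 16.1.4 excludes WOMACs taken more than 24 hours after patch removal or detachment, so some ET scores could be unusable anyway.
- SAP 16.1.5 and Appendix 3 already test missing-not-at-random assumptions, with shifts of up to 4 points on WOMAC pain and a copy-reference analysis.
- The percentages are shares of days, not of subjects. On the Days 1–83 base used for ECG, the WOMAC count is 33 of 83 = 40%. Withdrawal at a scheduled visit creates no duplicate, because the early-withdrawal page replaces the visit page (Protocol 8.2.3).

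These points stand and limit the WOMAC part to subjects who leave the study. The safety and QOL part is less affected. Listings keep the data, the ECG shift to worst overall result may still use ET recordings, and calling a Day 50 sample Week 8 is faithful in time. But the quantitative ECG table still omits every ET ECG before Day 74, and the SAP still does not say what becomes of QOL scores mapped to Weeks 1, 2 or 8. One could answer that the endpoint titles confine QOL to Weeks 4 and 12; then those scores are lost.

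**Conclusion.** The point holds as a gap in the windowing rules that is cheap to close. Followed as written, Table A sends ET ECG and weight to a visit that does not schedule them on 73 of Days 1–83, and ET laboratory and QOL records on 52 of 83. For subjects who leave the study, an ET WOMAC is dropped on 33 of 73 between-visit days when visits are on target (29 of 73 under the plus-one count). When the scheduled visit was early, the ET record can displace it.

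The WOMAC counts assume attendance on target days. Reading any of these counts as a share of leavers would also need ET to be equally likely on each day, which the documents do not state. The effect on the treatment estimate cannot be computed: sample size and effect size are redacted and no dropout rate is given. Bias in the primary comparison is therefore not shown. What is shown is that attendance day, rather than a pre-specified rule, decides which WOMAC of a leaver is analysed, and that leavers' ECG, weight, laboratory and QOL data are misplaced in, or absent from, the by-visit tables.

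**What to change.** Amend SAP 6.3 before unblinding:

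1. Add assessment-specific windows, so that ET laboratory and QOL records map only to Week 4 or Week 12. One split is Days 1–56 and Day 57 onward, since (28 + 84)/2 = 56.
2. Report ET ECG and weight, and laboratory values as well, in an added end-of-treatment row holding the last on-treatment value. Define it relative to the last patch removal, because a subject may stop patches and leave the study later.
3. For WOMAC, state which record prevails when an ET record and a completed scheduled visit share a window. Neither should displace the other without a pre-specified rule. Extend that rule to QOL, where the wider windows make sharing more likely.
4. Apply the intercurrent-event handling of SAP 16.1.4 by event date, before window selection, so that selection cannot remove a score the rule should act on.

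Moving the ET WOMAC to the next unattended visit is not required. It would let a Day 57 score stand for Week 12, 84 − 57 = 27 days early, against at most 73 − 56 = 17 days from target under the present Week 8 window. That resembles carrying a value forward and is a trade-off for the sponsor.

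The cost is wording, one more windowing table and an extra row in the safety shells; no new data are needed. The end-of-treatment row mixes exposure durations and should be labelled so. Some laboratory and QOL records will stand for a visit up to 28 days away (Day 56 against Day 28).

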### **Other Effects**

- A = slightly glazed appearance
- B = marked glazed appearance
- C = glazing with peeling and cracking
- F = glazing with fissures
- G = film of dried serous exudates covering all or part of the patch site
- H = small petechial erosions and/or scabs
- N = no other observations

During the Double-blind Treatment Phase at home, subjects will complete a questionnaire about skin irritation in the eDiary. Subjects will be asked to report any skin irritation to the site staff. Skin irritation reported by the subjects will be recorded as AEs. The investigator will assess any irritation observed at the patch application site at clinic visits. If the score of the dermal response and other effects are not 0 or N, it will be evaluated as AEs.

The subjects will be instructed to contact to their site and arrange for an unscheduled visit (i.e., site visit or virtual visit using remote video systems if available) when they experience any significant or intolerable irritation at home to manage the dermal reaction and evaluate it using the above scale.

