#### **10.3.2.4.3 Discomfort**

Discomfort will be assessed by the investigator or a designee using a predefined discomfort rating scale. The evaluator will ask the subject, “Are you experiencing any discomfort related to the patch?” If the answer is no, the overall level of discomfort will be rated as 0. If the answer is yes, the evaluator will then ask the subject to rate the discomfort as mild, moderate, or severe along with the description of the discomfort (e.g., itching, burning, pain, stinging, soreness, dryness, and other). Any discomfort mentioned should be recorded as AEs and rated as follows:

- 0 = No discomfort
- 1 = Mild discomfort

- 2 = Moderate but tolerable discomfort
- 3 = Severe, intolerable discomfort
- 4 = Patch not present

During the Double-blind Treatment Phase at home, subjects will complete a questionnaire about discomfort in the eDiary. If there is any discomfort, the description (e.g., itching, burning, pain, stinging, soreness, dryness, and other) will be recorded in the eDiary.

Discomfort reported by the subjects will be recorded as AEs.

The subjects will be instructed to contact to their site and arrange for an unscheduled visit (i.e., site visit or virtual visit using remote video systems if available) when they experience any significant or intolerable discomfort at home to manage the dermal reaction and evaluate it using the above scale.

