18.7.1.3 Irritation

Results of irritation assessment in clinic after patch removal as collected in *Dermal Evaluations* eCRF form using 2-part scales (Dermal Response and Other Effects) will be tabulated for each visit as a concatenated and combined score.

The following Berger and Bowman numerical scale is used to assess the Dermal Response:

- 0 = no evidence of irritation
- 1 = minimal erythema, barely perceptible
- 2 = definite erythema, readily visible; minimal edema or minimal papular response
- 3 = erythema and papules
- 4 = definite edema

Noven Pharmaceuticals, Inc.

Protocol HP-5000-US-07

Statistical Analysis Plan

Page 46 of 58

- 5 = erythema, edema, and papules
- 6 = vesicular eruption
- 7 = strong reaction spreading beyond the application site

The Other Effects will be scored via a letter as below:

- A (0) = slightly glazed appearance
- B (1) = marked glazed appearance
- C (2) = glazing with peeling and cracking
- F (3) = glazing with fissures
- G (3) = film of dried serous exudates covering all or part of the patch site
- H (3) = small petechial erosions and/or scabs
- N (0) = no other observations

[figure not shown]
The combined irritation score will be calculated as a numerical total; i.e., numerical “Dermal Response” score + numeric equivalent for the “Other Effects” lettered score (note that the “Other Notations” do not have numeric equivalents and do not contribute to the numeric Combined irritation score); e.g., 2N, 2A, and 3G will be reported as 2, 2, and 6 combined irritations scores respectively.

The frequency and percentage of subjects with patches in each combined and concatenated category will be summarized from the above scales at each visit and overall.

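### SAP 6.3 usually removes symptom-triggered irritation and discomfort grades from the by-visit dermal tables, and irritation has no worst-score summary to recover them

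*SAP*

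**What the plan says.** Protocol 10.3.2.4.2 (Irritation) tells subjects to contact the site and arrange an unscheduled visit, on site or by video, "when they experience any significant or intolerable irritation at home to manage the dermal reaction and evaluate it using the above scale". Protocol 10.3.2.4.3 (Discomfort) has the same instruction, "when they experience any significant or intolerable discomfort at home to manage the dermal reaction and evaluate it using the above scale".

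SAP 6.3 (Visit Windowing Conventions) states its scope: "Analyses presented by visit or study day will be based on the protocol defined scheduled visits including scheduled, unscheduled, and early discontinuation visits". Where a window holds more than one assessment, "the assessment closest to the Scheduled Target Day will be selected and assigned to that Scheduled Target Day"; where two or more are "equidistant from the Scheduled Target Day, the latest assessment will be selected". Table A sets the windows, for example Week 1 as "1 to 10 days relative to Day 0 datetime" and Week 2 as "11 to 17 days relative to Day 0 datetime". All records go into the listings.

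SAP 18.7.1 gives the dermal scales no exception:

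- Adhesion (18.7.1.1) and discomfort (18.7.1.2) each have, besides the by-visit rows, a summary of subjects by worst score.
- Irritation (18.7.1.3) does not. Its results "will be tabulated for each visit as a concatenated and combined score", and an overall row is mentioned without a derivation.
- Protocol 13.4.4.2.1 also requires the number and percentage of subjects with a combined irritation score of 3 or more. SAP 18.7.1.3 does not repeat it, although SAP 3.3 declares no changes from the protocol.

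**The concern.** These unscheduled grades exist because the subject found the reaction significant or intolerable. They compete for one place per window with a routine grade taken near the target day, and the winner is chosen by date. For example, a reaction graded 5G on Day 45 has a combined score of 5 + 3 = 8. If the routine Visit 7 on Day 56 is graded 0N, the Week 8 row shows 0N, a combined score of 0.

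Dermal irritation, discomfort and adhesion are named safety endpoints, and the graded tables are where a reader of a patch trial looks for how bad the reactions were. If triggered grades are more frequent in one arm, their removal from the by-visit rows narrows the displayed difference between arms. For irritation, nothing in the SAP guarantees that the grade reappears in another graded summary.

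**Working it through.** The plan states no figure on this point, so there is none to reproduce. The check applies the SAP 6.3 rule to whole days.

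**Inputs.** Windows and target days come from SAP Table A. Allowed deviations for scheduled visits come from the schedule of events in Protocol 10.2: ±2 days for Visits 4, 5 and 6, and ±7 for Visit 7. That table is broken in the available text, so these are the values as read. Week 12 is left out: Table A defines that window partly by the last patch removal, so how on-treatment days from Day 74 are assigned is not clear.

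**Assumptions.** Each window holds one scheduled and one unscheduled record, all days are equally likely, and days are counted from Day 0.

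**1. Scheduled visit on its target day.** Every other day is further away, so the unscheduled record always loses: 9 + 6 + 20 + 34 = 69 of 69 positions (100%).

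**2. Scheduled visit on any allowed day.** If the scheduled visit is *d* days early, the unscheduled record is kept on 2*d* days: 2*d* − 1 days are strictly nearer, plus the tied later day. If the scheduled visit is *d* days late, the unscheduled record is kept on 2*d* − 1 days, because the tie goes to the scheduled visit. Summing 4*d* − 1 over *d* = 1 to *w* gives *w*(2*w* + 1) pairs kept: 10 for *w* = 2 and 105 for *w* = 7.

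| Row | Days | Target | ± | Day pairs | Dropped | Share |
|---|---|---|---|---|---|---|
| Week 1 | 1–10 | 7 | 2 | 5 × 9 = 45 | 45 − 10 = 35 | 78% |
| Week 2 | 11–17 | 14 | 2 | 5 × 6 = 30 | 30 − 10 = 20 | 67% |
| Week 4 | 18–38 | 28 | 2 | 5 × 20 = 100 | 100 − 10 = 90 | 90% |
| Week 8 | 39–73 | 56 | 7 | 15 × 34 = 510 | 510 − 105 = 405 | 79% |
| All | | | | 685 | 550 | 80% |

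Week 8 supplies most of the pairs. Weighting windows by their days instead gives (7 + 4 + 18 + 27)/69 = 56/69 = 81%.

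**3. Subject withdraws at the unscheduled visit.** Under Protocol 10.1.5 this becomes an Early Termination visit, which includes a dermal assessment. With earlier visits on target and none later, the record is dropped only if it falls after the target day: 3 + 3 + 10 + 17 = 33 of 69 (48%). It is kept in 36 of 69 (52%).

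**4. Where the worst grade can still be tabulated.** For discomfort, the overall worst-score summary in SAP 18.7.1.2 can show it, although the SAP does not say that unscheduled records count. For irritation, no rule in SAP 18.7.1.3 says so.

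**The case against.** The strongest reply is that the reactions are not hidden. Irritation and discomfort reported by subjects are recorded as adverse events, and an abnormal clinic irritation grade is evaluated as one. The SAP tabulates application-site events separately (18.1.5), uses worst-case severity (18.1.1.1), summarises events leading to discontinuation (18.1.2) and summarises eDiary dermal reports (18.7.2). Unscheduled records are listed. All of this stands, so the gap lies in the graded tables and is not a loss of safety data. It does not close the gap: adverse event severity is a different scale and cannot reproduce Berger-Bowman grades or the 3-or-more count.

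A reader might infer that SAP 6.3 confines unscheduled data to listings. It does not. Such a record enters the by-visit analysis and is kept when it is alone in its window, nearer the target, or tied and later.

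A reader might also infer that the worst discomfort scores are lost altogether. Only the by-visit rows are exposed, because 18.7.1.2 has the overall worst-score summary.

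Finally, closest-to-target selection is a legitimate description of status at a visit. Worst-in-window is a maximum over windows of 10, 7, 21 and 35 days for Weeks 1, 2, 4 and 8, so longer windows would tend to show higher rates by construction. That is a fair reason not to replace every by-visit row.

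**Conclusion.** The concern holds for the by-visit irritation and discomfort tables. For subjects who continue, the rule usually removes the triggered grade: about 80% of day positions in Weeks 1 to 8, and 100% with the scheduled visit on target. For subjects who withdraw at that visit, about half of day positions are kept.

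These are shares of day positions under uniform timing with a scheduled record in the window, not shares of subjects. The documents give no frequency of unscheduled visits, so the number of subjects affected cannot be computed. That a triggered grade is the subject's worst is likely, but it is an inference.

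Irritation is the main gap, because its overall row has no worst-score rule and the protocol's 3-or-more count is missing from the SAP. It is tempting to conclude that the count will be understated. The documents do not support that: SAP 6.3 governs analyses by visit or study day, so the records feeding the overall row and the count are undefined, not shown to be the windowed ones.

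**What to change.** In SAP 18.7.1:

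- State that the overall irritation and discomfort summaries use each subject's worst post-baseline score over all records, including unscheduled and early termination visits.
- Restore the protocol's tabulation of combined irritation scores of 3 or more, on the same basis.
- State that discomfort code 4, which records that the patch is absent, is not ranked as the worst score. It is numerically above severe discomfort.
- For the by-visit tables, either give unscheduled evaluations their own row or add a worst-in-window display beside the closest-to-target one. Keeping the existing rows avoids the unequal-window problem.

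The cost is a few sentences and a little extra programming, and displayed irritation rates will be somewhat higher. Trial conduct and the efficacy analyses are unaffected.
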